3.3 SELECTION OF TRIAL POPULATION

A log of all subjects enrolled into the trial (i.e. who have signed informed consent) will be maintained in the ISF at the investigational site irrespective of whether they have been treated with investigational drug or not.

3.3.1 Main diagnosis for trial entry

Please refer to [Section 8.3.1](#) for the documentation requirements pertaining to the inclusion and exclusion criteria.

3.3.2 Inclusion criteria

1. Male or female subjects must have a diagnosis of asthma by a physician at least 3 months prior to screening (Visit 1). The diagnosis of asthma must meet the following spirometric criteria:
 - a. Pre-bronchodilator clinic measured $FEV_1 \geq 70\%$ of predicted normal (calculated by the Global Lung Function Initiative equation (GLI)) [[R15-0845](#)] measured ≥ 8 hours after the last use of short acting bronchodilator at the screening visit (Visit 1) and on the day of randomisation (Visit 2 i.e: Treatment Period 1 – Day 1)).
2. Age $\geq 18 \leq 60$ years. Subjects must be within the eligible age range on the day of signing informed consent.
3. Diagnosis of asthma must have been made before the subject's age of 40.

or

If the subject is ≥ 40 years and the diagnosis has not yet been recorded in the subject's medical files, the investigator should assess whether the subject's medical history (e.g. symptoms and prescribed medications) confirms the subject suffered from asthma since before the age of 40. If so, this subject may be considered for inclusion after consultation with the sponsor.

4. ACQ value < 1.5 at the screening visit (Visit 1).
5. PD20 (Provocative dose causing at least a 20% decline in FEV_1) at the screening visit (Visit 1) of methacholine $\leq 1\text{mg}$
6. Body mass index (BMI) ≥ 18.5 and $\leq 32.0 \text{ kg/m}^2$ at the screening visit (Visit 1)
7. Subjects must be able to perform all study related procedures and assessments, including pulmonary function tests, as required by the protocol.

3.3.3 Exclusion criteria

In order to be eligible for inclusion in the study, the subject must not present with any of the following:

1. Significant pulmonary diseases other than asthma (up to GINA treatment step 2) or other medical conditions* (as determined by medical history, examination** and clinical investigations at screening) that may, in the opinion of the investigator result in any of the following:
 - a) Put the subject at risk because of participation in the study

Proprietary confidential information © 2017 Boehringer Ingelheim International GmbH or one or more of its affiliated companies

- b) Influence the results of the study
- c) Cause concern regarding the subject's ability to participate in the study.

*e.g: cardiovascular, gastro-intestinal, hepatic, renal, metabolic, immunological, dermatologic, neurological, haematological, oncological, hormonal and psychiatric. A malignancy treated by resection, radiation or chemotherapy within the past 5 years. Subjects with treated basal cell carcinoma or fully cured squamous cell carcinoma are allowed to participate in the study.

** includes clinically relevant abnormal blood pressure, pulse rate or ECG findings.

2. Respiratory tract infection or asthma exacerbation in the 4 weeks prior to the screening visit (Visit 1). Subjects can be rescreened 4 weeks after resolution of the infection or exacerbation.
3. Hospitalisation for asthma exacerbation within 3 months or intubation for asthma within 3 years of the screening visit (Visit 1).
4. History of relevant orthostatic hypotension, fainting spells, or blackouts.
5. Major surgery (major according to the investigator's assessment) performed within 12 weeks prior to randomisation.
6. Clinically relevant (in the opinion of the investigator) abnormal baseline haematology, blood chemistry or urinalysis at the screening visit (Visit 1).
7. Serum potassium measurement above the ULN at the screening visit (Visit 1). Any value about the ULN excludes the subject irrespective of clinical relevance.
8. A history of significant alcohol or drug abuse within the last 2 years
9. Blood donation (more than 100mL within 30 days prior to the administration of trial medication or intended during the trial)
10. Subjects who have been treated with any of the following asthma medications in the given interval prior to Visit 1 (see [Section 4.2.2](#)):
 - Non-approved asthma therapies such as methotrexate,
 - Intravenous, intramuscular or oral corticosteroids
 - Inhaled corticosteroids (iCS) other than low dose iCS (defined as equivalent to equal to, or less than 250 µg fluticasone / day)
 - A long acting beta agonist or anticholinergic bronchodilator (Visit 1), including fixed dose beta agonist/inhaled corticosteroid combinations and oral bronchodilators.

Note: Withdrawal of bronchodilators or reduction in iCS dose is not acceptable unless for medical reasons.

- A biological based antagonist therapy including Omalizumab, or immune modulators
- Asthma controller medications (e.g: leukotriene modifier, methylxanthines, nedocromil or cromolyn sodium)
- Mucolytics

Proprietary confidential information © 2017 Boehringer Ingelheim International GmbH or one or more of its affiliated companies

- Systemically available immunomodulatory treatments for allergic rhinitis or atopic dermatitis.

11. Use of any diuretics (including loop diuretics or potassium sparing diuretics (such as amiloride), renin-angiotensin antihypertensive drugs in the 28 days prior to the screening visit (Visit 1))
12. Use of drugs that might reasonably influence the results of the trial or that might prolong the QT/QTc interval within 10 days prior to the randomisation visit (Visit 2 i.e: Treatment Period 1- Day 1).
13. A marked baseline prolongation of QT/QTcF interval (such as QTcF intervals that are repeatedly greater than 450 ms in males or repeatedly greater than 470 ms in females) or any other relevant ECG finding at screening and prior to randomisation
14. A history of additional risk factors for Torsades de Pointes (such as heart failure, hypokalemia, or family history of Long QT Syndrome)
15. Inability to comply with medication or dietary restrictions (see [Section 4.2.2](#)).
16. Intake of drugs with a long half-life (more than 24 hours) within at least 1 month of the screening visit (Visit 1) or less than 10 half-lives of the respective drug prior administration (except asthma or atopic disease modification and permitted concomitant medications as described in [Table 4.2.2.1:1](#))
17. Currently enrolled in another investigational device or drug study, or less than 30 days since receiving another investigational treatment(s)
18. History of relevant allergies/hypersensitivities (including allergy to the trial medication or its excipients)
19. Pregnant or nursing women or a positive serum pregnancy test at the screening visit (Visit 1)
20. Women of childbearing potential

All female subjects (and female partners of male subjects) are regarded as being of childbearing potential unless they are either post-menopausal or permanently sterilised. Post-menopausal is defined as having had, at least 12 months spontaneous amenorrhea with an appropriate clinical profile (age, vasomotor symptoms etc). Females may have been permanently sterilised by means of hysterectomy, bilateral salpingectomy, confirmed tubal occlusion or tubal ligation.

21. Male subjects who do not agree to minimise the risk of female partners becoming pregnant (including sperm donation) from the first dosing day until 3 months after the trial medication treatment has finished.

Male subjects with female partners of child bearing potential must use condoms plus any one other acceptable method of contraception together with their partners, from first dose until 3 months after the last dose of IMP. Alternatively, true heterosexual abstinence is also acceptable (this must be due to subject's lifestyle choice i.e. the subject should not become abstinent just for the purpose of study participation; withdrawal or calendar methods are not considered acceptable).

Acceptable methods of contraception for male subjects with female partners of childbearing potential include:

- Condoms
- Established hormonal contraception
- Intrauterine device (IUD)/intrauterine hormone-releasing system (IUS).

Male subjects with pregnant partners are excluded. Male subjects must not donate sperm until 3 months after the last dose of IMP.

22. Current smokers or ex-smokers who have given up smoking for < 12 months and / or have a smoking pack history of > 5 pack years (1 pack year = 20 cigarettes per day for 1 year of 5 cigarettes per day for 4 years)
23. Previous participation in this trial

3.3.4 Removal of subject from therapy or assessments

3.3.4.1 Removal of individual subjects

An excessive withdrawal rate can have a severe negative impact on the scientific value of the trial. Every effort should be made to keep subjects in the trial as scheduled. This includes careful subject selection and appropriate explanation of the trial requirements and procedures prior to enrolment as well as an explanation of the consequences of premature withdrawal.

An individual subject is to be withdrawn from trial treatment if:

a	FEV₁ falls ≥ 45% post methacholine challenge from post diluent value If the subject is symptomatic requiring SABA the study physician must be informed and the appropriate assessments taken, regardless of time-point. The PI should be informed of the situation as soon as possible and a decision will then be made by the PI as to whether the subject is to continue to receive MCh challenges at any further visits or be withdrawn.
b	The subject has a confirmed increase in serum potassium of ≥ 5.5 mmol/L in non-haemolysed blood.

Proprietary confidential information © 2017 Boehringer Ingelheim International GmbH or one or more of its affiliated companies

c	The subject shows relevant individual QT prolongation, i.e. a QTcF increase of greater 60 ms from baseline (pre-dose Day 1 of each Treatment Period)) in connection with absolute QT or QTcF greater than 500 ms, which has been confirmed by a repeat ECG recording.
d	The subject has an asthma exacerbation.
e	The subject withdraws consent for trial treatment or trial participation, without the need to justify the decision.
f	The subject needs to take concomitant drugs that interfere with the investigational product or other trial medication
g	The subject can no longer be treated with trial medication for other medical reasons (such as surgery, adverse events, other diseases, or pregnancy)
h	The subject has repeatedly shown to be non-compliant with important trial procedures and, in the opinion of both, the investigator and sponsor representative, is not willing or able to comply with the trial requirements in the future.

If the subject agrees, he/she will undergo the procedures for early treatment discontinuation and follow up as outlined in the [Flow Chart](#) (FC) and [Section 6.2.3](#).

For all subject the reason for withdrawal (e.g. adverse events) must be recorded in the CRF. These data will be included in the trial database and reported.

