- 1 This study (1363.7) will only start once healthy volunteers have been safely administered 100 and 400 µg b.i.d. of BI 443651 for 7days in a separate ongoing study (1363.2) i.e. no stopping criteria have been triggered in 1363.2.
- 2 Only mild, controlled, stable asthma subjects with well-maintained lung function will be included in the study i.e. subjects on prn SABA or low dose inhaled corticosteroid with an $FEV_1 \geq 70\%$ and no recent respiratory tract infection or exacerbation.
- 3 The study will be split into two parts ([see Section 3.1](#)) with an initial pilot (Part 1) to assess for gross adverse effects of BI 443651 on bronchoconstriction after MCh challenge. In Part 1, subjects will receive BI 443651 in a dose ordered fashion with either placebo **or** the lowest dose first followed by the higher doses and placebo (if not taken first). Individual subjects will not be dosed further if individual stopping criteria (including pulmonary function criteria) are triggered. Stopping criteria are described in detail in [Section 3.3.4](#).

The second part of the study (not necessarily dose ordered) will only proceed if no subjects triggered the first three discontinuation criteria following administration of BI 443651 during Part 1.

- 4 The subjects will be closely monitored throughout the treatment period with frequent evaluation of pulmonary function following MCh challenge. Subjects may only be discharged from clinic after medical assessment has been conducted. The subject's FEV_1 must have returned to $\geq 90\%$ of the first set of spirometry measurements performed that day before the subject can be discharged from the clinic. Rescue medication will be provided as required.
- 5 Safety laboratory testing will be performed during the study with a focus on electrolytes ([see Flow Chart](#)). The study will be stopped if, during Part 1 (pilot) at least 2 subjects in the current cohort or treatment period on active drug showed serum potassium levels $\geq 5.5\text{mmol/L}$ in non-haemolysed blood (confirmed by repeat). In Part 2 (main study), the study would be stopped if 4 subjects on active drug (independent of dose level) showed serum potassium levels $\geq 5.5\text{mmol/L}$ in non-haemolysed blood (confirmed by repeat).

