Placebo	100 µg	400 µg	1200 µg
100 µg	Placebo	1200 µg	400 µg
400 µg	1200 µg	Placebo	100 µg
1200 µg	400 µg	100 µg	Placebo

The first pilot part of the study will not be started until data from an ongoing multiple rising dose study (1363.2) in healthy volunteers is available from the first two dose groups (100 and 400 µg b.i.d. BI 443651). Only if BI 443651 has been safely administered in study 1363.2 and no stopping criteria have been met, will this study (1363.7) be started.

In Part 1, dose groups will be investigated consecutively in ascending order of doses with a dose escalation review between each treatment period. Data from each treatment level will be reviewed prior to progression to the next treatment level. Only if the previous dose of BI 443651 is safe and well tolerated, without meeting any stopping criteria in subjects administered BI 443651 ([see Section 3.3.4.1](#)), will the subsequent dose be administered ([Table 3.1:1](#)).

In addition a documented Safety Review by the Coordinating Investigator (or an authorised deputy) and appropriate personnel from the Sponsor must take place prior to initiation of Part 2 of the study. Only if BI 443651 is safe and well tolerated in all subjects in the pilot part without the specified number of subjects meeting any individual stopping criteria (see Section 3.3.4.1), will the transition to Part 2 occur.

An unscheduled safety review meeting can be requested anytime for any reasonable cause by the Principal Investigator (or an authorised deputy) or the sponsor of the study, e.g. because of any unforeseen adverse events, etc. Dose escalation or transition to Part 2 will only be permitted if no safety concerns exist in the opinion of the Principal Investigator (or an authorised deputy) and the Trial Clinical Monitor (or an authorised deputy). The minimum data set for review consists of the following data:

- Results from spirometry in all subjects included in the initial pilot part of the study
- AEs in all subjects including in the initial pilot part of the study, up to at least 48h post dosing (including clinically relevant findings from ancillary safety testing listed below) (Note: AEs may be ongoing at the time of Safety Reviews and AE information may be subject to change prior to Database Lock)
- Check of criteria for stopping subject treatment as per Section 3.3.4.1

Proprietary confidential information © 2017 Boehringer Ingelheim International GmbH or one or more of its affiliated companies

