3.3.4.2 Discontinuation of the trial by the sponsor

Boehringer Ingelheim reserves the right to discontinue the trial overall or at a particular trial site at any time for the following reasons:

1	Failure to meet expected enrolment goals overall or at a particular trial site
2	Emergence of any efficacy/safety information invalidating the earlier positive benefit-risk assessment that could significantly affect the continuation of the trial.
3	Violation of GCP, the CTP or the contract disturbing the appropriate conduct of the trial
4	New toxicological findings or serious adverse events invalidate the earlier positive benefit-risk assessment. More specifically, the trial will be terminated if two subjects have, at least, possibly related SAE or in case of the occurrence of three, at least, possibly related severe AEs. No further dosing, dose escalation or inclusion of any further

Proprietary confidential information © 2017 Boehringer Ingelheim International GmbH or one or more of its affiliated companies

	subjects (independent of dose level) will occur without approval of a substantial amendment.
5	
Part 1 (pilot study): At least 2 subjects* in the current cohort or treatment period on active drug showed serum potassium levels $\geq 5.5\text{mmol/L}$ in non-haemolysed blood (confirmed by repeat).
 
Part 2 (main study): At least 4 subjects* on active drug (independent of dose level) showed serum potassium levels $\geq 5.5\text{mmol/L}$ in non-haemolysed blood (confirmed by repeat).
 
* These are proposed thresholds for potential trial discontinuation however any and all individual occurrences of serum potassium levels $\geq 5.5\text{mmol/L}$ in non-haemolysed blood will be reviewed by the PI and sponsor medical team.

6	
At least 2 subjects independent of dose level on active drug showed relevant individual QT prolongation, i.e. a QTcF increase of greater 60 ms from baseline in connection with absolute QT or QTcF greater than 500 ms, which has been confirmed by a repeat ECG recording*
 
*These are proposed thresholds for potential trial discontinuation however any and all individual occurrences of QT prolongations will be reviewed by the PI and sponsor medical team

The Investigator / trial site will be reimbursed for reasonable expenses incurred in case of trial termination (except in case of the third reason).

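### Withdrawal criterion b words potassium 5.5 mmol/L as an increase with no baseline, while the other potassium rules use it as a level; taken literally, b cannot fire at 5.5

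*Protocol*

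**What the plan says.** Protocol section 3.3.4.1 lists the conditions under which an individual subject is to be withdrawn from trial treatment. Criterion b reads: "The subject has a confirmed increase in serum potassium of ≥ 5.5 mmol/L in non-haemolysed blood". It gives no baseline and no separate absolute value.

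The trial-level rules use the same figure differently. In section 3.3.4.2, item 5, the Part 1 rule is "At least 2 subjects* in the current cohort or treatment period on active drug showed serum potassium levels" at or above 5.5 mmol/L, and the Part 2 rule is "At least 4 subjects* on active drug (independent of dose level) showed serum potassium levels" at or above the same value. Both require non-haemolysed blood and a repeat. Section 2.3, item 5, has the same pair of rules; for Part 2 the study stops "if 4 subjects on active drug (independent of dose level) showed serum potassium levels" at or above 5.5. The footnote to item 5 of section 3.3.4.2 sends "any and all individual occurrences of serum potassium levels" of 5.5 mmol/L or more to the principal investigator and the sponsor's medical team for review.

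Two progression rules depend on the individual criteria. Under section 3.1, the next dose in Part 1 is given only if the previous one was tolerated "without meeting any stopping criteria in subjects administered BI 443651", with a reference to section 3.3.4.1. Under section 2.3, item 3, Part 2 "will only proceed if no subjects triggered the first three discontinuation criteria following administration of BI 443651 during Part 1". I read those three criteria as a, b and c of section 3.3.4.1.

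The SAP does not mention the potassium withdrawal rule.

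**The concern.** An increase of a stated amount is a difference between two measurements; a level is one measurement. Criterion b uses the language of a difference, while every other potassium rule in the protocol uses the language of a level with the same number. The row directly below shows how the protocol writes a genuine change rule: criterion c requires "a QTcF increase of greater 60 ms from baseline (pre-dose Day 1 of each Treatment Period" and then states the absolute QT or QTcF limit separately. Criterion b has neither part.

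This matters because section 2.3 names changes in serum electrolytes, rising potassium in particular, as the only systemic toxicity expected from the mechanism and the toxicology. The trial-level rules need at least two subjects in Part 1 or four in Part 2. For one subject, b is the only numeric rule that compels withdrawal. It is also the only route by which one subject's potassium result automatically reaches the Part 1 escalation check and the Part 2 gate. In Part 1 the active doses ascend from 100 to 400 to 1200 µg, so a subject who is not withdrawn usually goes on to a higher dose.

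**Working it through.** The plan gives no calculated figure to reproduce. The check compares the wording of the rules and then does simple arithmetic.

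**The rules side by side**

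| Place in protocol | Quantity at 5.5 mmol/L | Baseline named | Subjects needed | Action |
|---|---|---|---|---|
| 3.3.4.1 b | increase | none | 1 | mandatory withdrawal |
| 2.3 item 5 and 3.3.4.2 item 5, Part 1 | level | not needed | at least 2 | trial stop |
| 2.3 item 5 and 3.3.4.2 item 5, Part 2 | level | not needed | 4 (2.3), at least 4 (3.3.4.2) | trial stop |
| 3.3.4.2 item 5, footnote | level | not needed | 1 | review |

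The footnote in 3.3.4.2 describes the trial-level counts as proposed thresholds for potential discontinuation. No section restates b as a level.

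**Arithmetic.** Let *B* be the baseline.

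- Level needed for a literal increase of 5.5: *B* + 5.5.
- Rise present when the level is exactly 5.5: 5.5 − *B*.

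The literal rule fires at a level of 5.5 only if 5.5 − *B* ≥ 5.5, that is, only if *B* ≤ 0. It therefore cannot fire at 5.5 for any positive baseline. This step needs no assumption.

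The size of the gap does need a baseline. The documents give no potassium reference range: section 5.3.3 leaves it to the investigator site file, and exclusion criterion 7 only bars screening values above the upper limit of normal. I assume 3.5 to 5.0 mmol/L and show values on either side.

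| Assumed baseline (mmol/L) | Level needed, literal reading | Excess over 5.5 | Rise needed to reach 5.5 |
|---|---|---|---|
| 3.0 | 8.5 | 3.0 | 2.5 |
| 3.5 | 9.0 | 3.5 | 2.0 |
| 4.0 | 9.5 | 4.0 | 1.5 |
| 4.5 | 10.0 | 4.5 | 1.0 |
| 5.0 | 10.5 | 5.0 | 0.5 |
| 5.5 | 11.0 | 5.5 | 0.0 |

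Over 3.5 to 5.0, a subject who reaches a level of 5.5 has risen by 2.0 to 0.5 mmol/L. That is 2.0 / 5.5 = 36% down to 0.5 / 5.5 = 9% of the literal threshold.

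**Consequence for one subject.** Take a Part 1 subject with a confirmed 5.6 mmol/L after 100 µg, and no other subject affected. The two-subject rule is not met. Criterion b, read literally, is not met either. No numeric rule then requires withdrawal, and neither the escalation check nor the Part 2 gate is triggered through b.

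**The case against.** The strongest reply is that nobody would apply the literal reading. The shared number, unit, sample condition and confirmation requirement all point to a level. Non-haemolysed blood describes one sample, not a difference. The absence of a baseline, next to a criterion that has one, suggests that no change was meant. The literal reading would also make the scheme incoherent: the trial could stop for two or four subjects at 5.5 while no single subject was withdrawn below about 9. On this view the figures of 9.0 to 10.5 measure a reading that will not occur.

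There are also backstops. Every value of 5.5 or more is reviewed under the footnote in section 3.3.4.2. Local laboratory results govern dosing decisions, with potassium as the example (section 5.3.3). Criterion g permits withdrawal for other medical reasons. A joint safety review precedes each escalation and Part 2 (section 3.1). Timing helps too: the Flow Chart puts the discharge electrolyte sample at 33:00, after the last dose at 24:00, and the next period follows a washout of at least 14 days. A raised value at discharge can be reviewed before any further dose.

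Most of this stands. The intended meaning is fairly clear, and the practical risk is limited. Two things remain. The backstops call for review or judgement, whereas b is meant to make withdrawal automatic; section 3.3.4.1 itself urges every effort to keep subjects in the trial. And the washout allows time for a decision but does not supply the rule for making it, since b determines whether the subject enters the next period at all. The operative line of a mandatory safety rule should not have to be corrected by reference to other sections.

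**Conclusion.** Criterion b is wrong as written. It expresses as a change what sections 2.3 and 3.3.4.2 express as a level, and followed to the letter it cannot fire at 5.5 mmol/L for any positive baseline. The further statement that it would need 9.0 to 10.5 mmol/L, which is 3.5 to 5.0 above the other rules, rests on an assumed baseline of 3.5 to 5.0.

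The effect is confined to the loss of automatic action on a single subject under the literal reading, including the part that b plays in the Part 1 escalation check and the Part 2 gate. The latter depends on reading the first three discontinuation criteria as a to c. The trial-level potassium rules are not affected. The point should be corrected. It is certain as to the wording and modest as to the likely practical harm.

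**What to change.** In section 3.3.4.1, criterion b, replace *increase in serum potassium of* with *serum potassium level of*, keeping the requirements for confirmation and for non-haemolysed blood. The individual rule and the trial-level rules then refer to the same quantity, and b fires at 5.5. From an assumed baseline of 3.5 to 5.0 mmol/L, that corresponds to a rise of 2.0 to 0.5.

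The cost is one line in an amendment, with no change to endpoints, sample size or analysis.

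The rewording does not settle how many subjects block Part 2. Section 2.3, item 3, says none may trigger the criteria, whereas section 3.1 refers to a specified number. That is a separate ambiguity and needs its own clarification.
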